NPR	Norwegian Patient Register
NVAF	Non-valvular atrial fibrillation
OAC	Oral Anti-Coagulants
OS	Observational Study
PAS	Post-Authorization Study
PASS	Post-Authorization Safety Study

PDC	Proportion Days Covered
PIN	Personal Identification Number
SAP	Statistical Analysis Plan
SPAF	Stroke prevention in atrial fibrillation
STROBE	Strengthening the Reporting of Observational Studies in Epidemiology
US	United States
VKA	Vitamin K antagonists
WHO DD	World Health Organization Drug Dictionary

3. Responsible parties

3.2 Collaborator(s)/External partner(s)/Committee(s)

[REDACTED] [REDACTED]	Consultant Cardiologist	[REDACTED] [REDACTED] [REDACTED]	Principle Investigator
[REDACTED] [REDACTED]	Senior Researcher	[REDACTED] [REDACTED] [REDACTED] [REDACTED]	Project leader

4. Abstract

Acronym/Title	PROTECT-AF: A Post-marketing Retrospective nOn-interventional study using naTionwide registries and electronic medical records to investigate the real-life Effectiveness and major bleeding Complications of oral anTicoagulants in Norwegian non-valvular Atrial Fibrillation patients.
Protocol version and date	v 0.1, 06 September 2018
IMPACT study number	19468
Study type / Study phase	Observational, Phase IV PASS
Author	[REDACTED] [REDACTED] [REDACTED]
Rationale and background	Non-vitamin K antagonist oral anticoagulants (NOACs) are approved for the prevention of stroke and systemic embolism in adult patients with non-valvular atrial fibrillation (NVAF) as they reduce the risk of these events. However, the anticoagulant effect of the drugs must be balanced against a risk of bleeding complications especially in patients with renal impairment and elderly who represent a large group of those affected by NVAF(1-3).
Research question and objectives	
This population-based study will assess the effectiveness and safety of NOACs (rivaroxaban, dabigatran and apixaban compared to warfarin in OAC naïve NVAF patients in Norway. In addition, this study will serve as a pilot project to evaluate the ethical and operational feasibility as well as the usefulness of linking the EMR data to the Norwegian Health Registers.
 
Primary objective: to assess the incidence rates of:
 
 a. ischemic stroke (effectiveness) b. intracranial hemorrhage (safety) 
in OAC naïve NVAF patients who are dispensed individual NOACs for the first time and compare with the corresponding

	
rates in OAC naïve users of warfarin in a propensity score matched population.
 
Secondary objectives
 
• To assess the incidence rates of:
• overall stroke (ischemic, hemorrhagic, other unspecified) and systemic embolism outcomes;• myocardial infarction;• all-cause mortality;• major bleeding as defined by ISTH and the Cunningham algorithm (in a sub-set of patients; cohort 2) 
in OAC naïve NVAF patients who are dispensed individual NOACs and compare with the corresponding rates in OAC naïve users of warfarin in the overall population and separately for the elderly and renally impaired patient using a propensity score matched population.
 
• To describe and compare demographic and clinical characteristics (age, gender, CHA₂DS₂-VASc and HAS-BLED score, bleeding history, concomitant medications and co-morbidities) as well as drug utilization patterns of NVAF patients who initiated an OAC (NOACs and warfarin) in the study period. 
Several exploratory objectives aim to assess:
 
• differences in characteristics of NVAF patients receiving OACs or not• impact of adherence to NOACs on rates of ischemic stroke and bleeding• patient characteristics of NVAF patients receiving standard vs. reduced dose of NOACs and corresponding rates of ischemic stroke and bleeding in these sub-groups• validate data on indications and outcomes derived from the national registers using Electronic Medical Records
--	--------------------------------------------------------------------------------------------------------------------------------------------------------------------------------------------------------------------------------------------------------------------------------------------------------------------------------------------------------------------------------------------------------------------------------------------------------------------------------------------------------------------------------------------------------------------------------------------------------------------------------------------------------------------------------------------------------------------------------------------------------------------------------------------------------------------------------------------------------------------------------------------------------------------------------------------------------------------------------------------------------------------------------------------------------------------------------------------------------------------------------------------------------------------------------------------------------------------------------------------------------------------------------------------------------------------------------------------------------------------------------------------------------------------------------------------------------------------------------------------------------------------------------------------------------------------------------------------------------------------------------------------------------------------------------------------------------------------------------------------------------------------

	(EMR) available for a regional sub-set of patients (cohort 2).
Study design	This study will be a population-based retrospective cohort study on de-identified individual-level data extracted from national registers and EMRs in Norway. It will be based on two partly overlapping cohorts of patients, one utilizing only nation-wide health registers (cohort 1) and one cohort based on EMR data from selected hospitals in Norway combined with the registry data (cohort 2).
Population	The study population will comprise all adult OAC naïve NVAF patients in Norway who filled a prescription for an OAC (rivaroxaban, apixaban, dabigatran and warfarin) in the study period, defined as from 1 January 2014 to 30 June 2018 (or later depending on availability of data) and followed until outcome of interest, the end of the study period or death. This initiation of an OAC is the index event and requires that there is no previous prescription dispensed for an OAC in the preceding 365 days (counted from the date of the first dispensation backward to the end of OAC supply).
Variables	
Patient demographics (age, gender, migration status, place of birth and date of death), clinical characteristics on outcomes, comorbidities (ICD10 codes and procedure codes with date for admission and discharge) and prescription drugs used both OAC and relevant co-medication (ATC codes with date of dispensation, pack size, strength, number of units and so forth) will be retrieved from the nationwide registries. Risk scores (HAS-BLED and CHA2DS2-VASc) will be calculated.
 
More detailed demographic and clinical data such height, weight, smoking and alcohol use, laboratory values (INR, hemoglobin, s-creatinine) and dosing of OAC will be retrieved from the regional EMR data.

Data sources	De-identified individual level data from three nation-wide registers will form the basis for the analyses, the Norwegian Census Register (FRG), the Norwegian Prescription Database (NorPD) and the Norwegian Patient Register (NPR).

	
Additionally for cohort 2, in the South-East region of Norway, an automated EMR extraction tool will be deployed in order to retrieve additional clinical data that is not present in the nationwide registers.

Study size	
The study population will comprise all adult OAC naïve NVAF patients in Norway who filled a prescription for an OAC (rivaroxaban, apixaban, dabigatran, warfarin) in the study period, defined as from 1 January 2014 to 30 June 2018 (or later depending on availability of data). Based on the information regarding number of patients receiving listed drugs in the country, the sample size for the study will be approximately 70,000 patients.

Data analysis	
To compare warfarin with apixaban, dabigatran and rivaroxaban the incidence rates and corresponding 95% confidence intervals for ischemic stroke and intracranial hemorrhage will be calculated in a propensity score matched population.
 
Additionally the incidence rates of:
 
 • overall stroke and systemic embolism outcomes; • myocardial infarction; • all-cause mortality; • major bleeding 
will be calculated.

Milestones	
Protocol submission to IEC: Q3 2018 IEC approval: Q4 2018 Data inspectorate and registry holder approvals: Q1 2019 Analytical dataset available Q2: 2019 Preliminary results available on primary objective: Q2 2019 Final and complete report: Q1 2020

5. Amendments

None

6. Milestones

Table 1: Milestones

Milestone	Planned date
Protocol submission to PRC	5 April 2018
Ethical Committee approval	30 October 2018*
Registry holder approval	15 January 2019
Start of data collection	15 January 2019
End of data collection	15 March 2019
Analytical dataset available	15 April 2019
Preliminary data on primary objective	15 June 2019
Data Analysis Completed	15 October 2019
Registration in the EU PAS register	
Final report of study results	15 January 2020

*assuming one round of comments from Ethical committee

7. Rationale and background

NOACs are approved for prevention of stroke and systemic embolism in adult patients with non-valvular atrial fibrillation (stroke prevention in atrial fibrillation [SPAF]) as they reduce the risk of clot formation. However, the anticoagulant effect of the drugs must be balanced against a risk of bleeding complications especially in patients with renal impairment and elderly who represent a large group of those affected by Atrial Fibrillation (AF)(1-3).

In Norway, all Non vitamin K antagonist Oral Anti-Coagulants (NOACs) received full reimbursement for SPAF relatively soon after launch. There is no difference in reimbursement conditions between the different NOACs and they have been widely used in several indications including SPAF.

A recently published study based on the Norwegian population registry data indicated different incidence rates of bleeding for the different NOACs compared to warfarin.(4) The same study identified a significant proportion of patients receiving the reduced dose of NOACs, the

appropriateness however of the reduced dosing could not be assessed due to the lack of clinical information. Another clear limitation of this study is the lack of effectiveness data and information on adherence.

Norway has a relatively homogenous and stable population of just over 5 million and a publicly funded healthcare system. Health-related data is systematically captured in electronic format in several registers, including National Health Registers that contain data on hospitalizations, prescriptions as well as causes of death of all inhabitants. Hospital and primary care Electronic Medical Records (EMRs) information are also available. Inhabitants of Norway have a unique personal identification number (PIN) which is used to link information from the various health registers.

Extraction of large amounts of data from EMRs is often a limiting factor. An automated data extraction tool available in Scandinavia (Customised eXtraction Program [CXP], IQVIA) was shown to efficiently and reliably extract EMR data from hospitals and primary care clinics across the country in full adherence to the data protection rules(5). This unique methodology automatically extracts structured and unstructured EMR data for large numbers of patients and assigns identifiers that make cross-linking with registry data possible on an individual patient level, while ensuring patient anonymity. The methodology of the CXP tool was developed in Sweden and it has been applied in primary care in Norway. However it has not yet been applied with Norwegian hospital EMRs.

8. Research questions and objectives

This population-based study offers a unique opportunity to assess both the effectiveness and safety of NOACs (rivaroxaban, dabigatran, apixaban) compared to warfarin in OAC naïve NVAF patients in Norway. In addition, this study will serve as a pilot project to evaluate the operational feasibility as well as the usefulness of linking the EMR data to the Norwegian Health Registers.

8.1 Primary objective:

- To assess the incidence rates of:
 - a. ischemic stroke (effectiveness)
 - b. intracranial hemorrhage (safety)

in OAC naïve NVAF patients who are dispensed individual NOACs for the first time and compare with the corresponding rates in OAC naïve users of warfarin in a propensity score matched population.

8.2 Secondary objectives

- To assess the incidence rates of:

- overall stroke (ischemic, hemorrhagic, other unspecified) and systemic embolism outcomes;
- myocardial infarction;
- all-cause mortality;
- major bleeding as defined by ISTH and the Cunningham algorithm (in a sub-set of patients; cohort 2)

in OAC naïve NVAF patients who are dispensed individual NOACs for the first time and compare with the corresponding rates in OAC naïve users of warfarin in the overall and in a propensity score matched population.

- To describe and compare demographic and clinical characteristics (age, gender, CHA₂DS₂-VASc and HAS-BLED score, bleeding history, concomitant medications and co-morbidities) as well as drug utilization patterns of NVAF patients who initiated an OAC (NOACs and warfarin) in the study period.

8.3 Exploratory objectives (naïve OAC users)

- To compare demographic and clinical characteristics (age, gender, CHA₂DS₂-VASc and HAS-BLED score, bleeding history, concomitant medications and co-morbidities) and the incidence rates for ischemic stroke and intracranial hemorrhage in AF population that is not treated with OACs with AF population being treated with OACs.
- To investigate sub-groups of interest (patients > 75 years, renal impairment) in stratified analyses.
- To describe and compare adherence levels to NOACs among NVAF patients and assess whether different levels of adherence is associated with changes in the incidence rate of ischemic stroke and bleeding outcomes.
- To describe patient characteristics of NVAF patients receiving standard vs. reduced dose of NOACs and to estimate corresponding rates of ischemic stroke and bleeding
- To validate the diagnosis of NVAF, bleeding and stroke endpoints derived from the NPR data using EMR data.

9. Research methods

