9.2.1 Study time frame

For the main analysis, the study population will comprise all adult OAC naïve (no OAC prescription in the previous 365 days, counted from the date of the first dispensation backward to the end of OAC supply) NVAF patients in Norway dispensed a prescription for an OAC (NOAC or warfarin) for the first time in the study period (cohort 1a), defined as from 1 January 2014 to 30 June 2018 (or later depending on availability of data) and followed until endpoint of interest, the end of the study period or death. Patients will be censored at a switch or a discontinuation.

For exploratory analysis, a second study population (cohort 1b) will comprise all adult NVAF patients in Norway that did not receive an OAC (NOAC or warfarin) in the study period, defined as above.

The look-back period will be at least 5 years from the possible earliest index date of NOACs (1 January 2014) going back to 1 January 2009 (available data cut). The minimum follow-up period will be 1 month and the estimated mean follow-up time will be 18 months.

[figure not shown]

Figure 1: Study design

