9.2.2 Selection criteria

Depending on the data source, the following 2 cohorts will be recruited:

Inclusion criteria

Registry cohort (Cohort 1)

Cohort 1a:

- Age ≥ 18 at the date of first OAC dispensation (index date)
- Diagnosed with atrial fibrillation or flutter in the period 5-year pre-index period. Defined as ICD10 codes; I480 (paroxysmal AF), I481 (persisting AF), I482 (chronic AF), I483 (typical AF), I484 (atypical AF) or I489 (unspecified atrial fibrillation or flutter) as given by either NPR **or** as a OAC (warfarin, dabigatran, rivaroxaban or apixaban) dispensed on the reimbursement code for AF in NorPD (ICD10 I48 or ICPC-2 K78)
- Dispensation of a first-time prescription for an OAC during the study period 1 January 2014 to 31 May 2018. This initiation of an OAC is the index event and requires that there is no previous prescription for any OAC in the preceding 365 days (counted from the date of the first dispensation backward to the end of OAC supply).

Cohort 1b:

- Age ≥ 18 at the beginning of the study period (1 January 2014).
- Diagnosed with atrial fibrillation or flutter prior or during the study period. Defined as ICD10 codes; I480 (paroxysmal AF), I481 (persisting AF), I482 (chronic AF), I483 (typical AF), I484 (atypical AF) or I489 (unspecified atrial fibrillation or flutter) as given by NPR.
- No dispensation of a prescription for an OAC (warfarin, dabigatran, rivaroxaban or apixaban) during the study period 1 January 2014 to 30 June 2018. The index event will be the beginning of the study period (1 January 2014) and requires that there is no previous prescription for an OAC in the preceding 365 days.

EMR cohort (Cohort 2):

- Age ≥ 18 at the date of first OAC dispensation (index date).
- Diagnosed with atrial fibrillation or flutter in the 5-year pre-index period defined as one of the following ICD10 codes in the EMRs obtained from the hospitals in the South-

Eastern Health Region; I480 (paroxysmal AF), I481 (persisting AF), I482 (chronic AF), I483 (typical AF), I484 (atypical AF) or I489 (unspecified atrial fibrillation or flutter).

- Dispensation of a first-time prescription for an OAC (warfarin, dabigatran, rivaroxaban or apixaban) during the study period 1 January 2014 to 31 May 2018. This initiation of an OAC is the index event and requires that there is no previous prescription of any OAC in the preceding 365 days (counted from the date of the first dispensation backward to the end of OAC supply).

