9.7 Data analysis

All data analyses will be performed using SAS statistical software version 9.4., and will be reported in a manner consistent with the Strengthening the Reporting of Observational Studies in Epidemiology (STROBE) guidelines.

Descriptive statistics will be used to present the data where continuous variables will be summarized as mean, standard deviation, median, minimum and maximum. Categorical variables will be described by frequencies and related percentages. Summaries will be reported separately for the elderly +75 years (cohort 1 and 2) and patients with renal impairment (cohort 2). Annual frequency of different OAC treatment during the study period in addition to adherence to each NOACs (high, moderate, low, and poor) will be presented. Also a separate analysis will be done to characterize patients with NVAf who have not been treated with OAC.

In the following, cohort 1 (registry) and cohort 2 (EMR) will be analyzed separately, but using the same analytical approaches.

The analyses will be performed on the total sample as well as on a confounder adjusted sample. It has to be kept in mind that analyses based on the overall sample (non-confounder adjusted sample) is prone to bias (see section 9.9).

Three separate propensity score models will be conducted and a 1:1 matching will be performed for:

- warfarin vs apixaban
- warfarin vs dabigatran
- warfarin vs rivaroxaban.

No matching to compare the NOACs among each other (e.g. apixaban vs rivaroxaban) will be performed due to underlying differences in prescribing preferences of different NOACs.

The propensity scores (PS) will be based on demographic variables and clinically relevant medical history, e.g. cardiovascular risk factors, comorbidities and concomitant medications at baseline.

Patients who switch or discontinue the OAC treatment will be censored at the date of switch or discontinuation. It cannot be ruled out that the switch of OAC (censoring) could be informative, but it is handled as uninformative censoring in the analyses.

Detailed methodology for propensity score modeling, matching, handling of missing data, summary and statistical analyses in this study will be documented in a Statistical Analysis Plan (SAP), which will be dated, filed and maintained by the sponsor. The SAP may modify the plans outlined in the protocol; any major modifications of primary endpoint definitions or their analyses would be reflected in a protocol amendment.

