9.7.2 Further Analyses

The incidence rates and corresponding 95% confidence intervals for overall stroke (ischemic, hemorrhagic, other unspecified) and systemic embolism outcomes, myocardial infarction, all-cause mortality and major bleeding as defined by ISTH and the Cunningham algorithm (in a sub-set of patients; cohort 2) will be calculated for warfarin, apixaban, dabigatran and rivaroxaban cohorts.

Patients will be characterized according to demographic variables (age, gender), relevant medical history within 5 years prior to index date, different comorbidity risk scores (modified HAS-BLED, CHA2DS2VASC score, Charlson co-morbidity index), trends in OAC utilization from time of reimbursement, concomitant medications by OAC use and for NOACs-users, by the dose (standard or reduced) at start of follow up. Tests for differences between OAC sub-groups will be conducted using t-test, chi-square tests; the generalized linear model will be obtained to adjust for age and gender.

Additional analyses like a Cox proportional hazards regression models will be used to compare event rates of interest between the cohorts of users of different NOACs and warfarin adjusted for baseline covariates including age, gender, relevant medical history and concomitant medications. Hazard ratios with 95% confidence intervals for each study outcome will be presented (tables and Forest plots).

The occurrence of the first primary outcomes, as well as for the secondary outcomes among NVAF patients in warfarin versus NOACs will be described by Kaplan-Meier curves. The cumulative incidence of bleeding will be presented within different time windows (3m, 6m, 9m, 1 year, 2 years up until end of the follow-up).

Further details about the analysis and sensitivity analysis like Cox models evaluated within quintiles of PS probabilities can be found in the SAP.

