9.9 Limitations of the research methods

The strength of the study is that it retrieves data from mandatory and nationwide registries in a public health care system that covers all residents. As a result, the dataset will give us a complete picture of all hospitalizations and prescriptions dispensed nationwide for the entire study period. This complete coverage of data eliminates also selection bias and recall bias that is an apparent problem using other databases being based on selected hospitals, health insurance schemes, or self-reported questionnaires. On top of the nationwide registry data EMR data will give us deeper level phenotypic data such as laboratory values (INR, Hb), weight/height, smoking and alcohol abuse.

This study will measure drug exposure at the level of pharmacy dispensation and will have no information on patient's real OAC intake.

There is also a risk of misclassification related to coding errors of hospital admissions; however, for serious conditions like bleeding and stroke this unlikely a problem. Within the scope of the study a formal validation of the AF diagnosis in NPR will be performed against EMR.

Channeling bias (confounding by indication and severity) pertaining to newer drugs given to poor responding or more fragile patients compared to established drugs is a potential limitation. To mitigate this risk of bias we will use warfarin as reference category and also start the study period 1 January 2014, which will omit the first 6-12 months of NOACs use after reimbursement approval, i.e. when prescription patterns have not yet been established.

Estimates based on the overall population are prone to bias because the decision to give one treatment over the other depends on different baseline characteristics. Therefore any differences in the estimates for some treatment may be caused by the differences in the populations rather by the given treatment.

Due to the separate estimation of the propensity scores the population to compare warfarin vs apixaban may be very different from the population to compare warfarin vs rivaroxaban. Therefore no comparison between the NOACs among each other can be made.

Nonetheless, and although adjustment for a number of important and known baseline characteristics will be performed, some unmeasured and residual confounding related to prescribing behavior or patient characteristics cannot be fully accounted for.

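### Section 8.3 compares stroke and ICH rates between treated and untreated AF, but every adjustment the protocol names covers OAC users only

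*Protocol*

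**What the plan says.** Protocol section 8.3, first bullet, compares untreated with treated AF patients on baseline characteristics and also on the rates of ischemic stroke and "intracranial hemorrhage in AF population that is not treated with OACs with AF population being treated with OACs". These are the study's two primary outcomes. The primary objective (8.1) names a matched population and the secondary objectives (8.2) name the overall and matched populations. This bullet names no analysis population.

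The untreated patients are cohort 1b. Section 9.2.1: "For exploratory analysis, a second study population (cohort 1b) will comprise all adult NVAF patients in Norway that did not receive an OAC". Under section 9.2.2 they may be "Diagnosed with atrial fibrillation or flutter prior or during the study period", they must have no OAC dispensed from 1 January 2014 to 30 June 2018, and follow-up has one start for all of them: "The index event will be the beginning of the study period (1 January 2014").

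On analysis, section 9.7 promises results in the total sample and in a confounder-adjusted sample, and then states: "Three separate propensity score models will be conducted and a 1:1 matching will be performed for" warfarin against apixaban, dabigatran and rivaroxaban in turn. Section 9.7.2 adds Cox models comparing "event rates of interest between the cohorts of users of different NOACs and warfarin adjusted for baseline covariates". For the untreated, section 9.7 says: "Also a separate analysis will be done to characterize patients with NVAf who have not been treated with OAC". The abstract's version of the objective speaks of differences in characteristics and does not mention rates.

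**The concern.** The protocol sets a comparative objective on its two primary outcomes, then defines an adjusted sample that leaves out one side of the comparison. Followed literally, the contrast can come only from unadjusted rates. Section 9.9 warns of such rates: "Estimates based on the overall population are prone to bias because the decision to give one treatment over the other depends on" baseline characteristics. That sentence is written about the choice between treatments, but the reasoning applies equally to the choice between treating and not treating. The mitigation offered in 9.9 (warfarin as reference, start in 2014) addresses newer against established drugs and does nothing for treated against untreated.

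At stake is an exploratory result that could be read as the effect of anticoagulation on stroke or ICH when part of it is case mix. The protocol is also inconsistent about whether cohort 1b is there to be described or to be compared.

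**Working it through.** **1. Which adjustment reaches cohort 1b?**

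| Method | Section | Population | Includes 1b? |
|---|---|---|---|
| Three 1:1 propensity matches | 9.7 | warfarin vs each NOAC | No |
| Covariate-adjusted Cox | 9.7.2 | NOAC users vs warfarin users | No |
| GLM adjusted for age and gender | 9.7.2 | OAC sub-groups | No |
| Cox within propensity quintiles | 9.7.2 (detail in SAP) | the only propensity scores defined are the three above | No |
| Characterisation | 9.7 | untreated patients | Yes, descriptive only |

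The incidence rate ratios in section 9.7.1 are also set out only for warfarin against the three NOACs.

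**2. The plan's own figures.** The study-size figures in section 9.5 reproduce: 70,000 × 0.11 × 0.90 = 6,930; 70,000 × 0.17 × 0.90 = 10,710; 70,000 × 0.19 × 0.90 = 11,970. They all concern NOAC against warfarin. The protocol gives no size, event rate or risk profile for cohort 1b, so everything below rests on assumptions.

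**3. Case mix alone, stroke.** Assume no treatment effect and stroke rates per 100 patient-years of 0.6 (low risk) and 3.5 (others). With low-risk share s, rate = s × 0.6 + (1 − s) × 3.5.
- Treated, s = 8%: 0.08 × 0.6 + 0.92 × 3.5 = 3.268.
- Untreated, s = 15%: 0.15 × 0.6 + 0.85 × 3.5 = 3.065; ratio 3.268/3.065 = 1.07.
- Untreated, s = 35%: 0.35 × 0.6 + 0.65 × 3.5 = 2.485; ratio 3.268/2.485 = 1.32.

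If the untreated low-risk share were below 8%, the same formula would give a factor below 1.

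**4. Wider range.** For one binary risk marker with rate ratio R and prevalence p1 (treated) and p0 (untreated), crude ratio = true ratio × B, where B = [1 + p1(R − 1)] / [1 + p0(R − 1)].
- Stroke, with R from 2 to 5 and p1/p0 of 60/40%, 80/40% or 90/30%: B runs from 1.6/1.4 = 1.14 to 4.6/2.2 = 2.09. The crude ratio is 0.40-0.73 for a true ratio of 0.35, 0.57-1.05 for 0.50, 0.74-1.36 for 0.65 and 0.91-1.67 for 0.80.
- ICH, with a bleeding-risk marker in 10% of treated and 20-40% of untreated, R from 2 to 5: B runs from 1.4/2.6 = 0.54 to 1.1/1.2 = 0.92. The crude ratio is 0.67-1.15 for a true ratio of 1.25, 0.81-1.38 for 1.5 and 1.08-1.83 for 2.0.

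**5. What baseline adjustment would leave behind.** Cohort 1b counts from 1 January 2014 even when AF is diagnosed later. The period to 30 June 2018 is 54 months. If 30-60% of 1b were diagnosed during it, evenly over time and ignoring deaths, each would contribute on average half the period before diagnosis: 0.30 × 0.5 = 15% to 0.60 × 0.5 = 30% of person-time. Membership also depends on having no OAC at any later point. An untreated patient who has a stroke and then starts an OAC drops out of 1b, and the stroke goes with them. No covariate measured at baseline corrects either feature.

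**The case against.** The strongest reply is that the unadjusted reading is inferred from silence. The protocol never says the 1a against 1b comparison will be unadjusted. It leaves detailed methods to a SAP that is not shown, and the adjustment set for one exploratory contrast is ordinary SAP content. That stands as a limit on the claim. It does not remove the point, because the protocol itself lists which contrasts are adjusted and gives cohort 1b a descriptive role that conflicts with 8.3.

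It is also fair that the objective is exploratory, that 9.5 has no hypothesis to test, that bias in unadjusted estimates is disclosed in 9.7 and 9.9, and that no treated/untreated ratio is explicitly planned.

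A reader might infer two stronger things. One is that matching is the plan's only confounder control. It is not: 9.7.2 adds adjusted Cox models, a GLM and propensity quintiles, though all among OAC users. The other is that the comparison will reverse the apparent effect of OAC. The documents do not support that. Factors of 1.07-1.32 would reverse a protective stroke effect only if the true ratio exceeded about 0.94 (1/1.066) or 0.76 (1/1.315). In the wider range there is no reversal at a true stroke ratio of 0.35 or an ICH ratio of 2.0. Even the direction is open. In Table 4 the modified HAS-BLED and CHA2DS2-VASc scores share age, hypertension and prior stroke, so patients left untreated for bleeding risk may also carry high stroke risk.

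**Conclusion.** The point holds as a gap and an inconsistency in the protocol. Section 8.3 calls for a rate comparison, no named adjustment includes the untreated, and the abstract and 9.7 plan only to describe them. On the text as it stands, only the unadjusted sample supports the contrast.

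The bias cannot be sized or signed from the documents. The 1.07-1.32 shift in the stroke ratio depends entirely on the assumed rates (0.6 and 3.5 per 100 patient-years), the assumed low-risk shares (8% against 15-35%) and no treatment effect. Reversal of the apparent effect is arithmetically possible with a modest true effect or a strong imbalance, but it is not demonstrated. Because the objective is exploratory, this should be corrected but does not threaten the primary analysis.

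**What to change.** Reconcile section 8.3 with the abstract and section 9.7. Limit cohort 1b to description: characteristics, and event rates by CHA2DS2-VASc, HAS-BLED and age-sex stratum, with no treated/untreated ratio and no statement about effect. This costs about a sentence in 8.3 and one in 9.7.

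If a contrast is kept, report it only from an any-OAC-versus-none model adjusted for the Table 4 covariates and label it exploratory. First change cohort 1b so that follow-up does not start before AF diagnosis and membership does not depend on later non-use. An extra propensity model without that change would not be enough, and its result could look more credible than it is. The model uses data already held, but the cohort redefinition is real additional work. Under either option the simple crude comparison is given up.
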